## 5.2. Demographic and Other Baseline Characteristics

Summary descriptive statistics for demographic and other baseline characteristics will be reported for the FAS and SfAS analysis sets by treatment group and overall. The summary for FAS subjects will be by randomized treatment group and the summary for SfAS subjects will be by actual treatment group. Characteristics to be summarized include:

- Demographic: age, race, ethnicity, and sex.
- Targeted hearing loss history: when hearing loss started, ear(s) with hearing loss, etiology of hearing loss, other symptoms of hearing loss, and hearing aid use.
- Vital Signs: height, body weight, and BMI at screening.
- Pure Tone Average (0.5, 1, 2, and 4 kHz) at screening for the qualified ear.
- Bone Conduction Average (0.5, 1, 2, and 4 kHz) at screening for the qualified ear.
- Word Recognition number of recognized words at screening for the qualified ear.

Demographic and other baseline characteristic data will also be listed for subjects in the FAS.

Medical history and urine drug screen data will be listed for subjects in the FAS.

## 6. STUDY OPERATIONS

### 6.1. Protocol Deviations

All protocol deviations will be recorded in [REDACTED] clinical trial management system (CTMS) and reported in listings for randomized subjects. The listings will include the subject ID, treatment group, date of the deviation, protocol deviation text, and protocol deviation type. The medical and study team will perform a blinded review of the protocol deviations prior to the IA unblinding and database snapshot to classify the protocol deviations as major or minor. Protocol deviations that occur after unblinding for the IA will be evaluated for major/minor classification by the blinded medical and study team prior to study unblinding and database lock. The indicator identifying the deviation as major or minor will be included in the listings.

If the number of major protocol deviations is 10 or more, major protocol deviations will be summarized in tabular format by treatment group, including overall, and type of deviation for randomized subjects.

## 6.2. Randomization

Subjects will be randomized 1:1:1:1 to four treatment groups to receive multiple doses of FX-322 (0.2 mL) and/or placebo (0.2 mL). A single injection of FX-322 or placebo will be administered on Day 1 by intratympanic injection followed by subsequent injections of either FX-322 or placebo on Day 8, Day 15 and Day 21 as per treatment group. Randomized subjects will be allocated to each of 4 treatment groups (24 in each group).

Treatment Group Number (Label)	# of Subjects	Day 1	Day 8	Day 15	Day 21
1 (FX-322 1x)	24	FX-322	Placebo	Placebo	Placebo
2 (FX-322 2x)	24	FX-322	FX-322	Placebo	Placebo
3 (FX-322 4x)	24	FX-322	FX-322	FX-322	FX-322
4 (Placebo)	24	Placebo	Placebo	Placebo	Placebo

## 7. ENDPOINT EVALUATION

### 7.1. Overview of Efficacy Analysis Methods

#### 7.1.1. Multicenter Studies

Study subjects will be enrolled from multiple study sites. For the primary efficacy and safety analyses, study data will be analyzed and summarized as a whole, and no formal accommodation for site-to-site variation will be made.

Sensitivity analyses will be performed for select word recognition endpoints (percentage of recognized words, absolute percent change from baseline, relative percent change from baseline) to assess the possible presence and effect of site-to-site heterogeneity. Basic descriptive analyses of demographics, baseline characteristics or other assessments may be repeated for each site individually to support the word recognition sensitivity analyses.

#### 7.1.2. Assessment Time Windows

The following study visits are scheduled.

**Table 7-1 Study Visit Windows**

Visit	Visit Number	Assessment/Day	Target Day	Target Window	Analysis Window a
Screening	1	-30 to 0	0	0	<0
Baseline/ Treatment	2a	1	1	1	1
Treatment	2b	8	8	6-10 (+/- 2 days)	2-11
	2c	15	15	13-17 (+/- 2 days)	12-17
	2d	21	21	19-23 (+/- 2 days)	18-24
Follow-up	3	30	30	25-45 (+/- 15 days)	25-45
	4	60	60	45-75 (+/- 15 days)	46-75
	5	90	90	75-105 (+/- 15 days)	76-105
	6	120	120	105-135 (+/- 15 days)	106-135
	7	150	150	135-165 (+/- 15 days)	136-165
	8	180	180	165-195 (+/- 15 days)	166-195
	9	210	210	195-225 (+/- 15 days)	196-225

aAnalysis windows are defined using the mid-points between each scheduled visit, and will be used to map early termination or unscheduled visit data to scheduled visits.

All scheduled visit data per Protocol Version 4.0, including assessments performed outside the target window, will be included in summary tables, figures, and listings. Scheduled visit data will be presented according to the nominal case report form (CRF) recorded visit and not re-mapped according to the analysis windows in [Table 7-1](#). Early termination visit and unscheduled visit efficacy data will be mapped to scheduled visits using the analysis windows in [Table 7-1](#). Early termination visit and unscheduled visit efficacy data will be included in tables and figures if no scheduled visit data is available for the nominal CRF recorded visit. If more than one unscheduled assessment (early termination or unscheduled) is performed within an analysis window, the assessment performed closest to the target day will be used. For safety tables and figures, early termination visit and unscheduled safety data will not be mapped to scheduled visits using analysis windows. Data for assessments that were planned to be performed at on-site study visits in Protocol Version 2.0 and were removed in Protocol Version 3.0 due to the switch to telephone visits will be excluded from tables and figures. All data, scheduled and unscheduled, will be included in listings.

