| 1        | Updated date and version of protocol.                                  | Title Page, pg.1
Footer, every page  |
| 2        | Updated information regarding blinding roles on the study              | Section 8.7.1 Blinding pg. 27.          |
| 3        | Updated language to conduct data monitoring following the Day 90 visit | Section 14.1.6 Interim Analysis pg. 41. |

PROTOCOL Version 3.0 Amendments

| Item No. | Change  | Section and Page Number(s)   |
|----------|---|--|
| 1        | Updated date and version of protocol.                       | Title Page, pg.1
Footer, every page   |
| 2        | Updated visit type from clinic to phone.                    | Synopsis, pg. 4
Section 8.1 Overall Study Design and Plan, pg. 17.
Section 8.1.2 Schedule of Assessments, pg. 18.
Section 10.1.4 – 10.1.9 Visits, pgs. 30-31. |
| 3        | Removed assessments from visits                             | Section 11 Efficacy Measures pg. 32.
Section 12.1.7 Otoscopy, pg 34.
Section 12.1.8 Tympanometry, pg 34.   |
| 4        | Updated language around interim analysis                    | Section 14.1.6 Interim Analysis pg. 41.  |
| 5        | Updated how missing data will be handled                    | Section 14.2 Handling of Missing Subject Data and Subject Withdrawals pg. 42.  |
| 6        | Updated text for grammatical and capitalization consistency | Throughout Protocol  |

PROTOCOL Version 2.0 Amendments

| Item No. | Change  | Section and Page Number(s)  |
|----------|---|---|
| 1        | Updated date and version of protocol.   | Title Page, pg.1
Footer, every page  |
| 2        | Added information and signature for Sponsor Chief Medical Officer                                 | Sponsor Signature, pg. 2  |
| 3        | Defined “ear with worst hearing” as ear with the worst Screening pure tone average                | Section 2 Synopsis, pg. 4
Section 8.1, Overall Study Design and Plan, pg. 15
Section 8.7.5, Selection and Timing of Dose for Each Subject, pg. 26 |
| 4        | Clarified randomization should be $\geq 50\%$ correct, $< 50\%$ correct for the WR scores         | Section 8.1 Overall Study Design and Plan, pg. 15
Section 8.7.3 Method of Assigning Subjects to Treatment Groups, pg. 25                             |
| 5        | Updated stability criteria for clarification  | Section 8.1 Overall Study Design and Plan, pg. 15
Section 8.4.2. Inclusion Criteria, pg. 19  |

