### **Safety Endpoint(s)**

- Adverse events
- Changes from Screening in:
  - Otoscopy
  - Tympanometry

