Once a subject has been identified as meeting all inclusion/exclusion criteria, the qualifying ear with the worse hearing (ear with the worst Screening pure tone average) will be selected, unless a rationale exists to treat the other ear. The study treatment or placebo will be administered on Day 1, Day 8, Day 15, and Day 21. The placebo will be matched to FX-322 in consistency and color.

[figure not shown]
Each subject will be placed in the supine position. Topical anesthetic cream will be administered to the tympanic membrane. Under a microscope, a 25-gauge needle will be used to inject FX-322 or placebo into the middle ear at the junction of the posterior inferior and posterior superior quadrant with the needle tip directed towards the round window. The posterior superior quadrant should be avoided to prevent injury to the ossicles. After injection, the subject will continue to lie with the injected ear facing up for 10-15 minutes. The injections will be performed at an appropriate location designated by a Board-certified Otolaryngologist trained and experienced in performing intratympanic injections. Safety monitoring will include recording of adverse events (AEs), safety laboratory assessments, and monitoring of tympanometry and otoscopic exams.

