**Follow up:**

Subjects will be required to return to clinic for safety, otologic, and audiologic assessments at Days 15, 60, 90, 150, and 210 after the initial injection. Subjects will be contacted by phone for safety assessments at Days 30, 120, and 180.

Unscheduled visits may occur as needed. See the Schedule of Assessments for more information.

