### **12.1.7 Otoscopy**

Microscopic otoscopy will be included to specifically record any abnormalities of the external ear canal, tympanic membrane and middle ear and will be performed at Screening, prior to injection on Day 1, 8, 15, and 21 and at the Day 60, 90, 150, and 210 visits.

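### SAP 7.1.2 keeps otoscopy and tympanometry from clinic visits later changed to phone calls out of the by-visit and shift tables, so no scheduled ear examination is tabulated between the fourth injection and Day 60

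*SAP*

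**What the plan says.** The Version 3.0 amendment log in the protocol records two linked changes. One is "Updated visit type from clinic to phone". The other is "Removed assessments from visits", for which the log cites Section 11 (efficacy measures), 12.1.7 (otoscopy) and 12.1.8 (tympanometry). Protocol 8.1 now reads: "Subjects will be contacted by phone for safety assessments at Days 30, 120, and 180".

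The text under SAP Table 7-1 (Section 7.1.2) says that data for assessments planned on site in Version 2.0 that "were removed in Protocol Version 3.0 due to the switch to telephone visits will be excluded from tables and figures". The next sentence adds: "All data, scheduled and unscheduled, will be included in listings".

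On dosing, protocol 8.1 says: "The study treatment or placebo will be administered on Day 1, Day 8, Day 15, and Day 21". Protocol 12.1.7 places otoscopy at Screening, then "prior to injection on Day 1, 8, 15, and 21 and at the Day 60, 90, 150, and 210 visits". Tympanometry (protocol 10.1.3 and 12.1.8) is done at Screening, before the Day 15 injection, and then at Days 60, 90, 150 and 210.

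SAP 8.6.3 and 8.6.4 also keep unscheduled and early-termination examinations out of the otoscopy and tympanometry summary tables. Both measures are named safety endpoints in protocol 7.2, under "Changes from Screening in". Protocol 14.1.7.5 asks for their results by treatment group, ear and visit, with changes or shifts from baseline.

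**The concern.** Local safety of single and repeat dosing is a primary objective (protocol 7.1). The risks named in protocol 6.2 include eardrum perforation and middle ear infection, which otoscopy and tympanometry are meant to detect. Subjects who attended in clinic before the switch to phone calls probably had these examinations at Day 30. If so, the SAP drops from its summaries the only scheduled examinations made soon after the fourth injection.

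A pinhole perforation or an effusion seen at Day 30 and resolved by Day 60 would then appear in no otoscopy, tympanometry or shift table. SAP 8.6.3 has categories for perforations that are pinhole-sized or no more than 25% of the membrane. Only those above 25% are adverse events of special interest (protocol Section 13). A smaller one reaches a summary table only if it is also reported as an adverse event.

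**Working it through.** The plan gives no figure to reproduce, so the check is day arithmetic plus a comparison of the schedules.

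**Inputs**
- Last injection: Day 21 ± 2, so Days 19 to 23 (SAP Table 7-1).
- Visit 3, Day 30: window Days 25 to 45 (SAP Table 7-1).
- Visit 4, Day 60: target window Days 45 to 75 (SAP Table 7-1).

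**Gap from the fourth injection to the next scheduled ear examination** (examination day minus injection day)

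| Next examination | Nominal | Shortest | Longest |
|---|---|---|---|
| Day 60 (as tabulated now) | 60 − 21 = 39 | 45 − 23 = 22 | 75 − 19 = 56 |
| Day 30 (if tabulated) | 30 − 21 = 9 | 25 − 23 = 2 | 45 − 19 = 26 |

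The nominal difference is 39 − 9 = 30 days. The ranges assume that visits fall inside their windows.

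**What else could fill the gap in these tables.** Otoscopy at the Day 21 visit comes before the injection. Unscheduled and early-termination examinations are barred from the summaries. Nothing else scheduled falls between Day 21 and Day 60. For tympanometry, the last tabulated test before Day 60 is the pre-injection test on Day 15, which is 60 − 15 = 45 days earlier, with two injections in between.

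**Gap by dose group.** Nominal days from the last FX-322 dose to the next tabulated otoscopy, if the randomized schedule is followed:
- 1x: last active dose Day 1, next otoscopy Day 8; 8 − 1 = 7 days.
- 2x: last active dose Day 8, next otoscopy Day 15; 15 − 8 = 7 days.
- 4x: last active dose Day 21, next otoscopy Day 60; 60 − 21 = 39 days.

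In the 1x, 2x and placebo groups the Day 21 injection is placebo. For them the gap concerns only the effect of the injection procedure.

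**What cannot be computed.** The Version 2.0 schedule is not in the documents, nor is the number of subjects seen under it. That Day 30 had an ear examination follows from three facts together: the log says visits went from clinic to phone, it says assessments were removed and cites the otoscopy and tympanometry sections, and Day 30 is now a phone visit.

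**The case against.** The strongest reply is that clinically relevant findings reach the tables by another route. Protocol 9.1 requires any new clinically relevant finding to be reported as an adverse event, and protocol Section 13 defines adverse events broadly enough to include unfavourable signs. SAP 8.3 tabulates treatment-emergent events whatever the visit type, and ear-related ones also by treated and untreated ear. SAP 8.4.1 tabulates events of special interest. This stands, and it limits the loss to the by-visit and shift tables. It does not remove the loss: those tables count every recorded finding against the number of ears examined, which adverse event reporting does not do.

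A second reply is that tabulating to one common schedule is a pre-specified choice, applied alike to all groups in an exploratory study, and that columns holding only earlier subjects are not comparable with other visits. The rule gives no reason to suspect bias between groups. Partial numbers are a reason to label a descriptive column, but a weak one for omitting it.

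Third, the Day 30 and Day 60 target windows meet at Day 45, so for some subjects the gain would be small. For subjects seen only after the switch, no SAP wording can close the gap. Both points are correct.

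A reader might infer more than the documents support:
- *That the data vanish from the safety results.* They remain in listings, and reported events are tabulated.
- *That the excluded examinations are the ones closest to the last injection.* The Day 21 pre-injection otoscopy is closer and stays tabulated. Day 30 is the first scheduled examination after that injection.
- *That excluding the hearing tests thins the safety tables.* Word recognition, words-in-noise and audiometry are analysed as efficacy (SAP 7.3 to 7.6) and reach safety tables only through events of special interest.
- *That a known body of data is discarded.* Its existence at Day 30 is inferred, and its size is not given.

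**Conclusion.** The point holds within these limits. By rule, and without a safety exception, the SAP leaves out of its tables the otoscopy and tympanometry done at visits that later became phone calls. With the current schedule and the bar on unscheduled examinations, those tables then hold nothing between the fourth injection and Day 60.

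What is lost is the by-visit and shift summary of two named safety endpoints, for findings that resolved before Day 60 and were not reported as adverse events. Early otoscopy after the last active dose is thin mainly in the 4x group, the group with the most FX-322 exposure.

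The conclusion assumes that Version 2.0 had ear examinations at Day 30 and that some subjects attended in clinic before the switch. If few did, the practical loss is small, but so is the cost of showing the data.

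**What to change.** Amend the exclusion sentence in SAP 7.1.2 along these lines: otoscopy and tympanometry collected at clinic visits under Protocol Version 2.0 and later removed, at least those at Day 30, will be included in the descriptive by-visit and shift tables, or in a supplementary table, by actual treatment group and ear. The number of ears examined will be shown, with a note that only subjects seen before the switch contribute.

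Efficacy data from those visits can stay outside the repeated-measures models. Displaying Days 120 and 180 is optional, since those visits do not bear on the gap after the fourth injection.

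The cost is one change of SAP wording and some extra columns, up to three visits if all phone visits are shown, with small and partial numbers. No new data are collected and no inferential analysis changes.

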### 7.1.3. Timing of Analyses

The IA will be performed after all enrolled subjects complete Visit 5 (Day 90) and the database snapshot is completed.

All CSR analyses will be performed after the study is completed and the database is locked.

#### 7.1.4. Multiple Comparisons/Multiplicity

No adjustments for multiple comparisons will be made. All p-values will be considered descriptive.

#### 7.1.5. Model Fitting

The following types of models may be fit for the efficacy endpoints: Mixed-effect model for repeated measures (MMRM), generalized estimating equations (GEE), or logistic regression.

For the MMRM models, a single covariance structure will be applied to all MMRM analyses for an efficacy endpoint. Different covariance structures may be applied to different efficacy endpoints. For the Word Recognition in Quiet (WR) and Words-in-Noise (WIN) analyses, the covariance structure for each endpoint will be identified by comparing model fit for the relative percent change from baseline in percentage of recognized words using two different covariance structures (unstructured [UN] and autoregressive (1) [AR(1)]), as described in Section 7.3.4. For the audiometry analyses, the covariance structure will be identified by comparing model fit for the mean overall Pure Tone Average (PTA) using the two different covariance structures, as described for WR and WIN. For the Tinnitus Functional Index (TFI) analyses, the TFI total score will be used to identify the covariance structure for all TFI endpoint analyses. Covariance structures will also be identified for the Hearing Handicap Inventory for Adults (HHIA) and the Hearing Screening Inventory (HSI) analyses, separately, using the total scores. The covariance structures identified for the IA may be different than the covariance structures for the CSR analyses, based on the evaluation for model fit. Further details for each of the planned models and analyses are provided in subsequent sections.

Models and descriptive summaries for the IA will only include data through Visit 5 (Day 90). Data through Visit 9 (Day 210) will be included in the models and summarized descriptively for the CSR.

#### 7.1.6. Missing Data

Due to the exploratory nature of the study, no formal imputation on missing data will be performed. Missing data due to the COVID-19 pandemic will remain missing in the planned statistical summaries and analyses. Unless otherwise specified, incomplete data for the efficacy endpoints will be assumed missing at random (MAR) and analyzed using the MMRM approach.

For the WR and WIN, the number and percentage of subjects completing each word list at each visit will be summarized for treated ears by randomized treatment group for subjects in the FAS. For the audiometry endpoints, the number and percentage of subjects with non-missing, no response, or not done at each frequency and visit will be summarized for treated ears by randomized treatment group for subjects in the FAS.

Where recorded, visits impacted by the COVID-19 pandemic will be identified in data listings.

**Table 7-2 Efficacy Variables and Analysis Methods**

Efficacy Endpoint	Analysis Method(s)	Section
Word Recognition in Quiet		7.3
Number of recognized words	
 
• Descriptive summary for treated and untreated ears.
 
• MMRM in treated ears.
 
• Risk ratios of treated ears to untreated ears for all subjects, subjects with bilateral hearing loss, and subjects without bilateral hearing loss.
 
	7.3.1
Percentage of recognized words	
 
• Descriptive summary for treated and untreated ears.
 
• MMRM in treated ears.
 
• Sensitivity: Descriptive summary for treated ears by site.
 
	7.3.2
Absolute percent change from baseline in percentage of recognized words	
 
• Descriptive summary for treated and untreated ears.
 
• Line graphs (with standard error bars) for observed means for treated ears.
 
• Line graphs (with standard error bars) for adjusted (least squares) means for treated ears.
 
• MMRM in treated ears.
 
• Sensitivity: Descriptive summary for treated ears by site.
 
	7.3.3
Relative percent change from baseline in percentage of recognized words	
 
• Descriptive summary for treated and untreated ears.
 
• Line graphs (with standard error bars) for observed means for treated ears.
 
• Line graphs (with standard error bars) for adjusted (least squares) means for treated ears.
 
• MMRM in treated ears.
 
• Sensitivity: Descriptive summary for treated ears by site.
 
	7.3.4
Improvement $\geq 10\%$ (5 words) in percentage of recognized words	
 
• Descriptive summary for treated ears.
 
• GEE in treated ears.
 
	7.3.5
Arcsine-transformed WR	
 
• Descriptive summary for treated ears.
 
• MMRM in treated ears.
 
	7.3.6
WR categories	
 
• Descriptive summary for treated ears.
 
• Bar charts for treated ears.
 
	7.3.7

Efficacy Endpoint	Analysis Method(s)	Section
Shift in WR categories	
 
Descriptive summary for treated ears.
 
	7.3.8
Clinical Improvement in WR, using Thornton-Raffin Confidence Intervals (CI TR )	
 
Descriptive summary for treated ears.
 
Scatterplots for treated ears.
 
GEE in treated ears.
 
	7.3.9
Clinical Improvement in WR, using Carney Schlauch Confidence Intervals (CI CS )	
 
Descriptive summary for treated ears.
 
Scatterplots for treated ears.
 
GEE in treated ears.
 
	7.3.10
Incidence of incorrect phonemes	
 
Heat maps for treated ears.
 
	7.3.11
Words-In-Noise		7.4
Number of recognized words	
 
Descriptive summary for treated and untreated ears.
 
MMRM in treated ears.
 
Risk ratio of treated ears to untreated ears for all subjects, subjects with bilateral hearing loss, and subjects without bilateral hearing loss.
 
	7.4.1
Percentage of recognized words	
 
Descriptive summary for treated and untreated ears.
 
Line graphs (with standard error bars) for observed means for treated ears (at each signal-to-noise ratio).
 
MMRM in treated ears.
 
	7.4.2
Absolute percent change from baseline in percentage of recognized words	
 
Descriptive summary for treated and untreated ears.
 
Line graphs (with standard error bars) for observed means for treated ears.
 
Line graphs (with standard error bars) for adjusted (least squares) means for treated ears.
 
MMRM in treated ears.
 
	7.4.3
Relative percent change from baseline in percentage of recognized words	
 
Descriptive summary for treated and untreated ears.
 
Line graphs (with standard error bars) for observed means for treated ears.
 
Line graphs (with standard error bars) for adjusted (least squares) means for treated ears.
 
MMRM in treated ears.
 
	7.4.4
Improvement $\geq 10\%$ (5 words) in percentage of recognized words	
 
Descriptive summary for treated ears.
 
GEE in treated ears.
 
	7.4.5

Efficacy Endpoint	Analysis Method(s)	Section
Spearman-Kärber estimates of dB thresholds for word recognition (25 th , 50 th (median) and 75 th percentiles)	
 
• Descriptive summary for treated ears.
 
• Scatter plots for treated ears.
 
• MMRM in treated ears.
 
	7.4.6
Improvement $\geq 3$ dB shifts in median Spearman-Kärber estimates	
 
• Descriptive summary for treated ears.
 
• GEE in treated ears.
 
	7.4.7
Incidence of incorrect phonemes	
 
• Heat maps for treated ears.
 
	7.4.8
Pure Tone Audiometry		7.5
Air Conduction (AC) and Bone Conduction (BC) audiometry dB hearing thresholds by frequency	
 
• Descriptive summary for treated and untreated ears.
 
• MMRM in treated ears.
 
	7.5.1
AC and BC Improvement $\geq 10$ dB from baseline for two contiguous frequencies	
 
• Descriptive summary for treated ears.
 
• GEE in treated ears.
 
	7.5.2
AC and BC Improvement $\geq 15$ dB from baseline for any frequency	
 
• Descriptive summary for treated ears.
 
• GEE in treated ears.
 
	7.5.3
AC and BC Composite Improvement	
 
• Descriptive summary for treated ears.
 
• GEE in treated ears.
 
	7.5.4
Mean overall Pure Tone Average (PTA) (AC over 0.5, 1, 2, and 4 kHz) and Bone Conduction Average (BCA) (BC over 0.5, 1, 2 and 4 kHz)	
 
• Descriptive summary for treated ears.
 
• MMRM in treated ears.
 
• Descriptive summary of shift from baseline in PTA categories for treated ears.
 
	7.5.5
Mean low AC dB hearing threshold (AC only over 0.25, 0.5, 1, and 2 kHz frequencies)	
 
• Descriptive summary for treated ears.
 
• MMRM in treated ears.
 
	7.5.6

Efficacy Endpoint	Analysis Method(s)	Section
Mean high AC dB hearing threshold (AC only over 3, 4, 6, and 8 kHz frequencies)	
 
• Descriptive summary for treated ears.
 
• MMRM in treated ears.
 
	7.5.7
Air-Bone Imbalance at 0.5, 1, 2, 3, and 4 kHz	
 
• Descriptive summaries for treated ears.
 
	7.5.8
Composite Endpoint		
Composite WR, WIN and Pure Tone Audiometry Endpoint	
 
• Descriptive summary for treated ears.
 
• Logistic Regression in treated ears.
 
	7.5.9
Extended High Frequency Audiometry (EHFA)		7.6
AC audiometry dB hearing thresholds by frequency	
 
• Descriptive summary for treated and untreated ears.
 
• MMRM in treated ears.
 
	7.6.1
AC Improvement $\geq 10$ dB from baseline for two contiguous frequencies	
 
• Descriptive summary for treated ears.
 
• GEE in treated ears.
 
	7.6.2
AC Improvement $\geq 15$ dB from baseline for any frequency	
 
• Descriptive summary for treated ears.
 
• GEE in treated ears.
 
	7.6.3
AC Composite Improvement	
 
• Descriptive summary for treated ears.
 
• GEE in treated ears.
 
	7.6.4
Mean dB hearing threshold (AC over 9-16 kHz)	
 
• Descriptive summary for treated ears.
 
• MMRM in treated ears.
 
	7.6.5
Shift from no signal to any signal by frequency	
 
• Descriptive summary for treated ears.
 
	7.6.6
Shift from no signal to any signal in two contiguous frequencies	
 
• Descriptive summary for treated ears.
 
	7.6.7
Shift from no signal to any signal in three contiguous frequencies	
 
• Descriptive summary for treated ears.
 
	7.6.8

Efficacy Endpoint	Analysis Method(s)	Section
Tinnitus Functional Index		7.7
Mean total score, individual subscale scores, and loudness score	
 
• Descriptive summary.
 
• MMRM for total score and loudness score.
 
	7.7.1
Change from baseline in mean total score, individual subscale scores, and loudness score	
 
• Descriptive summary.
 
• MMRM for total score and loudness score.
 
• Correlation analyses.
 
	7.7.2
Hearing Handicap Inventory for Adults		7.8
Mean total score and individual subscale scores	
 
• Descriptive summary.
 
• MMRM.
 
	7.8.1
Change from baseline in mean total score and individual subscale scores	
 
• Descriptive summary.
 
• MMRM.
 
• Correlation analyses.
 
	7.8.2
Hearing Screening Inventory		7.9
Mean total score	
 
• Descriptive summary.
 
• MMRM.
 
	7.9.1
Change from baseline in mean total score	
 
• Descriptive summary.
 
• MMRM.
 
• Correlation analyses.
 
	7.9.2

